7.1.5.2. Incomplete Dates

If the onset date of the AE is incomplete and the AE stop date is not prior to the first dosing date of filgotinib in the core studies or GLPG0634-CL-205, then the month and year (or year alone if month is not recorded) of onset determine whether an AE is treatment emergent. The event is considered treatment emergent if both of the following 2 criteria are met:

- The AE onset is the same as or after the month and year (or year) of the first dosing date of filgotinib in the core studies or GLPG0634-CL-205, and
- The AE onset date is the same as or before the month and year (or year) of the date corresponding to 30 days after the date of the last dose of filgotinib in GLPG0634-CL-205

An AE with completely missing onset and stop dates, or with the onset date missing and a stop date later than the first dosing date of filgotinib in the core studies or GLPG0634-CL-205, will be considered to be treatment emergent. In addition, an AE with the onset date missing and incomplete stop date with the same or later month and year (or year alone if month is not recorded) as the first dosing date of filgotinib in the core studies or GLPG0634-CL-205 will be considered treatment emergent.

7.1.6. Summaries of Adverse Events and Deaths

Treatment-emergent AEs will be summarized based on the Safety Analysis Set.

7.1.6.1. Summaries of AE incidence in Combined Severity Grade Subsets

The number and percentage of subjects who experienced at least 1 TEAE will be provided and summarized by SOC, HLT, PT, and treatment group. For other AEs described below, summaries will be provided by SOC, PT, and treatment group:

- TEAEs of Grade severe
- TEAEs of Grade moderate or higher
- All TE treatment-related AEs
- TE Treatment-related AEs of Grade severe
- TE Treatment-related AEs of Grade moderate or higher
- All TE SAEs
- All TE treatment-related SAEs
- All TEAEs leading to premature discontinuation of any study drug
- All TEAEs leading to premature discontinuation of study
- All TEAEs leading to temporary interruption of any study drug
- All TE SAEs leading to death (ie, outcome of death)

A brief, high-level summary of AEs described above will be provided by treatment group and by the number and percentage of subjects who experienced the above AEs. All deaths reported in the study will be also included in this summary.

Multiple events will be counted only once per subject in each summary. Adverse events will be summarized and listed first in alphabetic order of SOC and HLT within each SOC (if applicable), and then by PT in descending order of total frequency within each SOC. For summaries by

severity grade, the most severe grade will be used for those AEs that occurred more than once in an individual subject during the study.

In addition to the above summary tables, all TEAEs and TE treatment-related AEs will be summarized by PT only, in descending order of total frequency.

In addition, data listings will be provided for the following:

- All AEs, indicating whether the event is treatment emergent
- All AEs of Grade severe
- All AEs of Grade moderate or higher
- SAEs
- Deaths
- All SAEs leading to death (ie, outcome of death)
- AEs leading to premature discontinuation of any study drug
- AEs leading to premature discontinuation of study
- AEs leading to temporary interruption of any study drug

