 - Subjects with persistent abnormal laboratory values associated with the use of the study medication (including but not limited to hematology, liver and renal function values) during one of the 2 core studies (GLPG0634-CL-203 or GLPG0634-CL-204), according to the investigator's clinical judgment.
 - Subjects with diagnosis since the inclusion to GLPG0634-CL-203 or GLPG0634-CL-204 core studies of rheumatic autoimmune disease or inflammatory joint disease other than RA, except for secondary Sjögren's syndrome.
- Primary Endpoint:** Safety and tolerability of long-term dosing of filgotinib 200 mg q.d. and 100 mg b.i.d.

- Secondary Endpoints:** Evolution in the percentage of subjects achieving American College of Rheumatology (ACR)20, ACR50, ACR70, and ACR-N responses; European League Against Rheumatism (EULAR) responses; ACR/EULAR remission, clinical disease activity index (CDAI), simplified disease activity index (SDAI), and the disease-activity score based on 28 joints (DAS28 c-reactive protein [CRP]) every 12 weeks or until the Final Visit or the Early Discontinuation Visit (EDV). Change from Baseline in the Quality of Life (functional assessment of chronic illness therapy [FACIT] fatigue scale and 36-item short form health survey [SF-36] scores) every 48 weeks or until the Final Visit or the EDV.
- Safety Analysis:** The safety analysis will be performed for all subjects who used the study medication at least once in this study. Assessment of treatment-emergent adverse events, and of changes from Baseline in laboratory parameters, vital signs, physical examination, and electrocardiograms.
- Efficacy Analysis:** ACR20, ACR50, ACR70, ACR-N, EULAR response, and ACR/EULAR remission, DAS28(CRP), components of the ACR, and DAS28, CDAI, SDAI, and Quality of Life data (FACIT fatigue scale and SF-36 questionnaire) at each post dosing visit (as appropriate) will be analyzed descriptively. Changes from Baseline will be examined to check for evolution over time in treatment effect.

4 Table of Contents

1	Protocol Approval Signatures	2
2	Study Personnel	3
3	Synopsis	4
4	Table of Contents	7
	LIST OF TABLES	9
5	List of Abbreviations and Definition of Terms	10
6	Introduction	12
6.1	Rheumatoid Arthritis	12
6.2	Background on Filgotinib	13
6.3	Background - Pre-clinical Studies	13
6.3.1	Physical, Chemical and Pharmaceutical Properties and Formulations	13
6.3.2	Nonclinical Pharmacology	14
6.3.2.1	Primary and Secondary Pharmacology	14
6.3.2.2	Safety Pharmacology	14

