The following decision choice will be used by the investigator to describe the causality assessment between the reported event and the investigational medicinal product.

- Unrelated: No relationship between the AE and the administration of investigational product; related to other etiologies such as concomitant medications or subject's clinical state.
 - Unlikely: Event or laboratory test abnormality, with a time to study medication intake that makes a relationship improbable (but not impossible). Disease or other drugs provide plausible explanations.
 - Possible: Event or laboratory test abnormality, with reasonable time relationship to study medication intake which could also be explained by disease or other drugs. Information on drug withdrawal may be lacking or unclear.
 - Probable: Event or laboratory test abnormality, with reasonable time relationship to study medication intake. Event unlikely to be attributed to disease or other drugs. Response to withdrawal is clinically reasonable and rechallenge not required.
-

- Certain: Event or laboratory test abnormality, with plausible time relationship to study medication intake which cannot be explained by disease or other drugs. Response to withdrawal is plausible (pharmacologically, pathologically). Event definitive pharmacologically or phenomenologically (ie, an objective and specific medical disorder or a recognized pharmacological phenomenon). Rechallenge satisfactory, if necessary.

Action Taken Regarding Investigational Product

The action taken must be described by choosing among:

- Dose not changed: In case no action is taken regarding the study medication.
- Study medication permanently withdrawn: In case a subject is permanently withdrawn from the study.
- Study medication temporarily withdrawn: In case the study medication is temporarily withdrawn.
- Dose reduction: If a subject's daily dose is adjusted from 200 mg to 100 mg (q.d., once daily in the morning).
- Not applicable: Other situations (eg, in case an AE started after the last study medication administration).

Outcome

Each AE must be rated by choosing among:

- Recovered/Resolved.
- Recovered/Resolved with sequelae.
- Not recovered/Not resolved.
- Fatal.
- Recovering/Resolving.
- Unknown.

8.8.1.2.1.2 Recording Adverse Events

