8.9.1.3 Safety Variables

Clinical safety will be evaluated by assessing treatment-emergent AEs (TEAEs), physical examinations, laboratory assessments, ECG results, and vital signs results. The safety analysis may combine the data of all 3 studies (GLPG0634-CL-203, GLPG0634-CL-204, and GLPG0634-CL-205).

A treatment-emergent analysis of AEs will be done, based on the start date of the AE. TEAE (AE and SAE) preferred terms, intensity, frequency, relationship to study medication, dose reductions, and temporary/permanent treatment stops will all be tabulated. An additional analysis based on patient-years of exposure may be added when deemed useful.

Original results and changes from baseline will be summarized for all laboratory, vital signs, and ECG parameters, intended to detect any changes in safety parameters that could be attributed to GLPG0634 dosing. No imputations will be done for safety data in cases where subjects discontinued the study prematurely.

Further subgroup analyses (e.g., a selection of TEAEs with an onset date during the first weeks or months, or a division according to the mean actual dose) and exploratory analyses may be added when deemed appropriate.

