7.7. Changes From Protocol-Specified Safety Analyses

There are no deviations from the protocol-specified safety analyses.

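### SAP 7.1.6.1 has no summary of TEAEs leading to dose reduction, which Protocol 8.9.1.3 says will be tabulated, and SAP 7.7 declares no deviation

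*SAP*

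**What the plan says.** **Protocol.** The Synopsis gives the primary endpoint as "Safety and tolerability of long-term dosing of filgotinib 200 mg q.d. and 100 mg b.i.d". If a subject does not tolerate 200 mg daily, the investigator may reduce to 100 mg q.d. (8.6.6). The adverse event form records the action taken. Dose reduction is one of its codes, used when the "daily dose is adjusted from 200 mg to 100 mg", and it is separate from temporary and permanent withdrawal (8.8.1.2.1.1). For the analysis of TEAEs, 8.9.1.3 states that "dose reductions, and temporary/permanent treatment stops will all be tabulated".

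**SAP.** Section 7.1.6.1 lists the TEAE subsets to be summarised. The ones about drug action are "All TEAEs leading to premature discontinuation of any study drug" and "All TEAEs leading to temporary interruption of any study drug"; a further one covers discontinuation of the study. The listings follow the same pattern and begin with "All AEs, indicating whether the event is treatment emergent". Section 7.7 then says: "There are no deviations from the protocol-specified safety analyses".

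**The concern.** The protocol makes a firm commitment and the SAP does not carry it out, while stating that nothing has changed. A reader of the study report who relies on SAP 7.7 would not know that a promised tabulation had been left out.

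The omitted item bears on the primary endpoint. In this study, reduction to 100 mg q.d. is the protocol's own response to intolerance of the 200 mg daily dose. Below 100 mg q.d. the only step left is to stop, temporarily or permanently (Protocol 8.6.6). The SAP therefore reports the stopping steps but not the reduction step. A subject whose event was handled by reduction alone, with no later interruption or stop for a TEAE, appears in no summary of drug action.

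**Working it through.** There is no planned figure to reproduce. The check sets the two documents side by side.

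**Step 1: is the commitment mandatory?** Protocol 8.9.1.3 uses permissive wording for some analyses, such as rates by patient-years and subgroups ("or a division according to the mean actual dose"). Dose reductions are not among these; they are in the sentence saying what will be tabulated.

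**Step 2: compare item by item.**

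| Item in Protocol 8.9.1.3 | Supplied by SAP 7.1.6.1? |
|---|---|
| Preferred terms | Yes, tables by PT |
| Intensity | Yes, severe; moderate or higher |
| Frequency | Yes, number and percentage of subjects |
| Relationship | Yes, treatment-related subsets |
| Permanent stops | Yes |
| Temporary stops | Yes |
| Dose reductions | No |

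Covered: 7 − 1 = 6 of 7 items. Among the three drug actions (reduction, temporary stop, permanent stop): 2 of 3. The section has 11 bulleted summary subsets and 9 listings, and none of them concerns dose reduction.

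**Step 3: could the interruption table include reductions?** No. The protocol's form codes the two actions separately, so an event coded only as a dose reduction would not be picked up as an interruption.

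**Step 4: does any other SAP output supply it?**

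- SAP 1.2 mentions dose decrease only when describing the design.
- SAP 3 labels listings with the assigned treatment group, which does not change after a reduction.
- SAP 3.2 groups subjects as filgotinib with MTX or filgotinib monotherapy. Each group pools 100 mg q.d., 100 mg b.i.d. and 200 mg q.d.
- SAP 4.2 reports duration of exposure, not dose.
- The all-AE listing may show the action taken, but the SAP specifies only a treatment-emergence flag. A listing is also not a tabulation.
- The SAP does not take up the protocol's optional division by mean actual dose.

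**Step 5: which protocol version?** SAP 1 says that the SAP is based on Amendment 3. The supplied protocol is Amendment 4. The visible part of its change log shows no change to 8.9.1.3, but the start of the log and Amendment 3 itself are not available.

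**The case against.** **No event is lost.** This is correct. An event handled by reduction stays in the overall TEAE tables, in the severity, relatedness and seriousness tables where it qualifies, and in the all-AE listing. A reader might infer that tolerability of 200 mg daily goes unreported, or that the discontinuation table is understated. The documents support neither. Leaving such an event out of the discontinuation table is right; what is missing is one companion table. The counts of 0 in 11 and 0 in 9 also make the gap look larger than it is, because most of those subsets have nothing to do with drug action. Two of three actions is the fairer measure.

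**SAP 7.7 may be true of the protocol it was written for.** A reader might infer that the statement is simply false. That can be shown only against Amendment 4. A change to 8.9.1.3 between the two amendments seems unlikely, but it cannot be excluded. The SAP is inconsistent with the current protocol either way.

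**The protocol sentence is general.** It prescribes no layout and leaves detail to the SAP. That stands: a simple count by preferred term would satisfy it, and no dedicated listing is required. It does not excuse having no count at all.

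**A table by the SAP's own groups would say little about the two regimens in the primary endpoint.** This also stands. The groups of SAP 3.2 do not separate 200 mg q.d. from 100 mg b.i.d., and they include US males limited to 100 mg q.d. (SAP 1.2), who cannot be reduced further. The remedy has to deal with both.

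**Conclusion.** The mismatch is real and minor. Following the SAP exactly would omit one tabulation that the current protocol requires, in a study whose primary endpoint is safety and tolerability, and the SAP does not declare the omission. The effect is confined to the dose-reduction part of the tolerability report. The documents do not say how many subjects were reduced for a TEAE, so no percentage can be given, and the number could be small. Efficacy results are unaffected, and no formal test is planned.

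The conclusion assumes that the current protocol is the right standard of comparison. Saying that SAP 7.7 was already inaccurate when written would need the further assumption that Amendment 3 carried the same sentence. That is likely but unverified.

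**What to change.** 1. In SAP 7.1.6.1 add a subset for all TEAEs leading to dose reduction of study drug: number and percentage of subjects, by PT and treatment group. Add one corresponding line to the high-level AE summary.
2. Take the events from the dose-reduction action code on the GLPG0634-CL-205 AE records. Include core-study events carried over onto those pages (Protocol 8.7.1.1), provided they meet the TEAE definition in SAP 7.1.5.1.
3. Use as denominator the subjects who started GLPG0634-CL-205 at 200 mg daily, which leaves out US males limited to 100 mg q.d. Footnote this, since the other lines use the whole Safety Analysis Set. Preferably show 200 mg q.d. and 100 mg b.i.d. starters separately.
4. Do not merge reduction, interruption and discontinuation into one combined percentage. The interruption and discontinuation summaries count TEAEs from the first filgotinib dose in the core studies or the extension, whereas the documents define the reduction code only for GLPG0634-CL-205. The protocol does not ask for such a line.
5. If the table is not wanted, state the omission and the reason in SAP 7.7. If the SAP is already final, state it in the CSR, as SAP 1 provides for later changes.

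The cost is one table, one summary line and one footnote. The action code is already collected, so no protocol amendment, new procedure or new data is needed.

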7.1.7. Adverse Events of Special Interest

Events of interest will be identified by the use of either SMQs or MSTs. However, should additional cases not detected by the predefined search term listings be identified during the clinical review process, these cases will also be reported by respective category.

7.1.7.1. Adjudication Committee for MACE

An independent cardiovascular safety endpoint adjudication committee (CVEAC) will be formed to periodically review and adjudicate all potential major cardiovascular adverse events (MACE) events. MACE events are defined as cardiovascular death, non-fatal myocardial infarction and non-fatal stroke.

To identify the MACE event, the following potential cases will be adjudicated:

- All deaths
- Cardiovascular events (meeting serious criteria)
- Myocardial infarction (Narrow)

- Unstable angina (meeting serious or hospitalization criteria)
- Transient ischemic attack
- Stroke
- Cardiac failure (meeting serious or hospitalization criteria)
- Percutaneous coronary intervention

Potential MACE will be identified using MedDRA search listing (MST) searches.

The CVEAC will review those potential MACE and related clinical data to determine whether a MACE has occurred.

The CVEAC's role and responsibilities and the data to be provided to the CVEAC are described in a mutually agreed upon CVEAC charter. The CVEAC charter defines the CVEAC membership, adjudication process, meeting logistics, and meeting frequency.

The number and percentage of subjects with positively adjudicated MACE will be summarized by treatment group using the PT term.

A by-subject listing for all patients who have potential MACE at any time will be provided.

7.1.7.2. Other Adverse Events of Special Interest

In addition to general safety parameters and MACE, safety information on other adverse events of special interest (AESIs) will also be analyzed. AESIs will be identified by either laboratory results, standardized MedDRA queries (SMQs), or sponsor defined MSTs, or a combination of these methods as indicated below.

- All infections (defined as all PTs in the Infections and Infestations SOC)
- Serious infections (defined as all PTs in the Infections and Infestations SOC that are SAEs)
- Infections of special interest as defined below
 - a) Herpes zoster
 - b) Active tuberculosis
 - c) Opportunistic infections
 - d) Hepatitis B or C infections
- Deep vein thrombosis (DVT) and pulmonary embolism (PE)

- Malignancy (including lymphoma; not including nonmelanoma skin cancer)
- Nonmelanoma skin cancer
- Gastrointestinal (GI) perforations

The number and percentage of patients with aforementioned events of special interest will be provided by the PT term for each AE of special interests.

A by-subject listing for all patients having AE of special interests at any time will be provided for each AE of special interests.

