8.1 Overall Study Design and Plan

This is a multicenter, open-label, long-term follow-up study in subjects with RA. An approximate total of 600 subjects will be enrolled in the study after they have completed one of the previous 2 core studies (GLPG0634-CL-203 or GLPG0634-CL-204). All subjects will start the study at the same dose level (filgotinib 200 mg daily, administered either as 200 mg q.d. or as 100 mg b.i.d., depending on the dosing regimen [frequency of intake of active IMP] that was administered during the preceding core study). The investigator may decide to decrease the daily dose of filgotinib to 100 mg q.d. in case of intolerance or safety reasons. Subjects will return to the 200 mg GLPG0634 daily dose after the reasons for decreasing the dose have resolved, and at the investigator's discretion. Subjects can also continue filgotinib 100 mg q.d. when deemed necessary by the investigator. Subjects coming from the GLPG0634-CL-204 study will be allowed to start MTX treatment, if deemed necessary according to the investigator's clinical judgment.

Subjects have entered the study at Entry Visit on Day -1, which occurred on the same day as the last visit from the previous core study (GLPG0634-CL-203 or GLPG0634-CL-204). Subjects participating in the study have been requested to attend Quarterly Evaluation Visits (QEVs) every 12 weeks. If necessary, unscheduled visits can occur in between the scheduled study visits, for instance, in case the dose of study medication is to be adapted. In case of early withdrawal, an Early Discontinuation Visit (EDV) will be scheduled.

The duration of the participation and treatment for any subject in this study is expected to last for several years (from Entry visit to Follow-up Visit) and will be determined by the sponsor based on the following:

- Open label period (approximately 96 months).
- Marketing Application Approval/Withdrawal in Country of Residence.
- Applicable local reimbursement procedures are in place.

Sites will be notified once these criteria are met.

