2.4. Week 156 Analysis

A planned Week 156 analysis will be conducted after all subjects have either completed their Week 156 visit or prematurely discontinued from the study.

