4.2. Extent of Filgotinib Exposure

Total duration of exposure to filgotinib will be defined as (last dose date of filgotinib in GLPG0634-CL-205 - first dose date of filgotinib in the core studies or GLPG0634-CL-205 + 1), regardless of any temporary interruptions in administration and will be expressed in weeks using up to 1 decimal place (eg, 4.5 weeks).

If the last filgotinib dosing date is missing, the latest date among the clinical visit date and laboratory sample collection date that occurred during the on-treatment period will be used.

If subjects are continuing on study drug, The data cutoff date will be used to impute the last dosing date for the calculation of the duration of exposure to filgotinib.

The total duration of exposure to filgotinib will be summarized using descriptive statistics and using the number (ie, cumulative counts) and percentage of subjects exposed for filgotinib baseline and every 12 weeks afterwards.

Summaries will be provided by treatment group for the Safety Analysis Set. No formal statistical testing is planned.

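### Adverse events are planned only as crude percentages of subjects, with no rate or confidence interval, although follow-up runs from early discontinuation to about 96 months

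*SAP*

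**What the plan says.** The primary objective is long-term safety and tolerability (Protocol 7.1; SAP 1.1). The adverse-event outputs are these:

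- **TEAEs, SAEs, discontinuations and deaths (SAP 7.1.6.1):** "The number and percentage of subjects who experienced at least 1 TEAE will be provided", with the subsets handled in the same way. "Multiple events will be counted only once per subject in each summary".
- **MACE (SAP 7.1.7.1):** "The number and percentage of subjects with positively adjudicated MACE will be summarized by treatment group using the PT term".
- **Other events of special interest (SAP 7.1.7.2):** "The number and percentage of patients with aforementioned events of special interest will be provided by the PT term".

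SAP section 3 gives categorical variables a count and a percentage and no interval. I found no rate, person-time denominator or cumulative incidence for adverse events in the SAP. Section 3.5.3 mentions a time-to-event analysis only as an example within a record-selection rule.

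Protocol 8.9.1.3 leaves the matter open: "An additional analysis based on patient-years of exposure may be added when deemed useful". SAP 4.2 covers exposure separately: "The total duration of exposure to filgotinib will be summarized using descriptive statistics", together with cumulative counts and percentages of subjects exposed at 12-week steps, by treatment group.

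The open-label period is about 96 months, and subjects may leave early (Protocol 8.1). Two main looks are planned. For the first, "A planned Week 156 analysis will be conducted after all subjects have either completed their Week 156 visit or prematurely discontinued" (SAP 2.4); the final analysis follows study completion (SAP 2.5). Results are shown for two groups defined by source study, with MTX and monotherapy (SAP 3.2).

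**The concern.** The percentage of subjects with at least one event mixes the risk per unit time with the length of time observed. When follow-up is unequal this has three consequences.

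- At an unchanged hazard, the Week 156 and final percentages differ simply because the second look is later.
- If retention differs between the two source-study groups, their percentages differ even at the same underlying rate. No formal comparison is planned, but the columns will be read side by side.
- For a rare event with no cases, the table shows 0% and does not say how large a rate the data exclude. That is often the main question in a long-term safety study.

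At stake is how the central safety tables can be read. The counts themselves are valid.

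**Working it through.** **Design figure.** The only sample-size figure is the expected roll-over, 0.7 × (595 + 280) = 612.5, which reproduces the stated 612 (SAP 1.3; Protocol 8.9.2). It carries no event rate or precision target. Actual enrolment was 739 (Protocol 8.3.1).

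**Assumptions.** The documents give no event or dropout rates. I assume a constant first-event rate r of 2 per 100 patient-years (PY), with 0.5 as a lower case, and annual dropout p of 0, 10% or 20%, so d = −ln(1 − p). T is 3 years (approximately Week 156) or 8 years (96 months). Only extension time is modelled.

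**1. Crude percentage.** 100 × r/(r + d) × (1 − exp(−(r + d)T)), with r = 0.02:

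| Annual dropout | 3 years | 8 years | Ratio |
|---|---|---|---|
| 0 | 5.82% | 14.79% | 2.54 |
| 10% | 5.00% | 10.10% | 2.02 |
| 20% | 4.26% | 7.05% | 1.65 |

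The true rate is the same in every cell. If one group had 10% dropout and the other 20%, the 8-year ratio would be 10.10/7.05 = 1.43, against a true ratio of 1.

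**2. What the exposure table recovers.** Mean exposure over 8 years is (1 − exp(−dT))/d = 5.406 years at 10% dropout and 3.730 at 20%. Dividing the crude percentage by it:

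- r = 2 per 100 PY: 10.10/5.406 = 1.87 and 7.05/3.730 = 1.89 per 100 PY, which is 6.6% and 5.5% below the truth.
- r = 0.5 per 100 PY: the shortfall is 1.7% and 1.4%.

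So the spurious 1.43 ratio disappears. The rate is slightly low because total exposure is not censored at first event, and it has no interval.

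**3. Zero events.** The exact two-sided 95% upper limit is −ln(0.025)/PY = 3.689/PY. For group sizes I assume equal roll-over from the two core studies: 739 × 595/875 ≈ 503 and 739 × 280/875 ≈ 236. At 8 years:

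| Set | PY, full retention | Limit per 100 PY | PY, 20% dropout | Limit per 100 PY |
|---|---|---|---|---|
| Pooled, 739 | 5,912 | 0.06 | 2,756 | 0.13 |
| About 503 | 4,024 | 0.09 | 1,876 | 0.20 |
| About 236 | 1,888 | 0.20 | 880 | 0.42 |

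None of these limits is printed under the current plan.

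**4. What the proposed rate would show.** Expected time at risk is N × (1 − exp(−(r + d)T))/(r + d). With r = 0.02 and 8 years:

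- 503 subjects, 10% dropout: 2,541 PY and 51 events (rounded), 2.01 per 100 PY (exact 95% CI 1.49 to 2.64).
- 236 subjects, 20% dropout: 832 PY and 17 events (rounded), 2.04 per 100 PY (1.19 to 3.27).

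The two rates agree, as they should, and the intervals show how much less the smaller group can say.

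**The case against.** The best defence is that the planned outputs already supply most of what is needed. SAP 4.2 gives exposure by group, including cumulative counts every 12 weeks, so differing retention would be visible. Exposure and the TEAE window (SAP 7.1.5.1) start at the same first filgotinib dose and end 30 days apart. By-subject listings of events are also planned. The study is open-label and descriptive, and the protocol permits a patient-years analysis. Much of this stands: step 2 shows that a careful reader can get close to the rate. What it does not supply is an interval, time censored at first event, or a rule fixed in advance. An optional clause leaves the choice until this open-label study's data have been seen. A rate with an interval is itself descriptive, so the absence of testing is no reason to omit it.

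A reader might also infer more than the documents support:

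- *That the SAP breaches the protocol.* It does not. The patient-years analysis is optional, so the statement in SAP 7.7 that there are no deviations is not contradicted on this point.
- *That the Week 156 and final figures cannot be compared at all.* They are not directly comparable as percentages, but both can be set against exposure.
- *That inflation between looks is always about 2.5-fold.* That requires full retention for 8 years; with dropout it is nearer 1.65 to 2.02 in this example.
- *That retention does differ between the groups.* Nothing in the documents says so; the 10% and 20% are illustrative.
- *That the whole safety analysis ignores time.* Laboratory values, vital signs and ECG are summarised by visit and are outside this point.

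**Conclusion.** The point holds and should be fixed. The adverse-event part of the primary safety evaluation is planned only as crude percentages whose size depends on follow-up, with no rate and no interval. At an assumed 2 per 100 PY, the 3-to-8-year rise with unchanged risk is 2.54-fold with full retention and 1.65- to 2.02-fold with 20% to 10% annual dropout. The exposure table mitigates this: a rate derived from it is low by only 1.4 to 6.6% over 8 years in the cases with dropout examined here. The clearest remaining gap is precision. With no cases, the 8-year upper limits would be 0.06 to 0.13 per 100 PY pooled, but up to 0.42 in the smaller group, and both would print as 0%. The figures rest on constant hazards, assumed event and dropout rates, and equal roll-over from the core studies. That the SAP contains no rate or interval rests on none of these.

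**What to change.** In SAP 7.1.6 and 7.1.7, keep the n (%) tables and add first-event incidence per 100 patient-years with exact Poisson 95% intervals, by group and pooled, for deaths, SAEs, adverse-event discontinuations, serious infections, MACE and the other listed events of special interest. Specify:

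- **Time at risk:** from first CL-205 dose to the earliest of first event, last dose + 30 days, last contact (last recorded visit) or data cutoff. Last contact matters because adverse events are recorded only to the Follow-up Visit (Protocol 8.8.1.2.1.2), about 2 weeks after the Final Visit or EDV. Starting at CL-205 entry avoids counting core-study time during which a subject who withdrew could not have joined the Safety Analysis Set.
- **Onset dates:** an imputation rule for incomplete or missing dates. SAP 7.1.5.2 classifies such events as treatment-emergent or not but assigns no date.
- **Earlier events:** whether a subject whose event first occurred in the core study stays at risk for that event in CL-205.
- **Presentation:** core-period events shown separately, with a footnote that rate numerators are smaller than the n (%) counts, whose window opens at first filgotinib dose in a core study.
- **Limitations:** a constant hazard is assumed, and selection of core-study completers remains.

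The cost is SAP wording, a few extra tables and the date-handling rules. No new data collection or analysis set is needed.
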